5.4 Study Duration

5.4.1 Approximate Duration of Subject Participation

The median progression-free survival for these patients is in the order of 8-12 months, and the median overall survival is in the order of 14-18 months. Subject participation will be from

registration to progression, death or 26 months after the enrollment of the last study participant. This includes registration, study treatment, postoperative phase, adjuvant therapy, and follow-up.

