mg. The exact dose administered should be recorded in the CRF. Each daily dose should be given with the least number of capsules.

Prior to each treatment cycle with temozolomide a complete blood count (CBC) will be obtained (within 72 hours prior to dosing). Patients will be suggested to fast at least 2 hours before and 1 hour after temozolomide administration. Water is allowed during the fast period. Patients will be instructed to swallow the capsules whole, in rapid succession, without chewing them. Treatment should be given at night. If vomiting occurs during the course of treatment, no re-dosing of the patient is allowed before the next scheduled dose.

Antiemetic prophylaxis with a 5-HT3 antagonist is strongly recommended and should be administered 30 to 60 minutes before temozolomide administration.

Patients will be treated with post-radiation post-operative temozolomide for 6-12 cycles unless there is evidence of tumor progression or treatment-related toxicity

Pneumocystis carinii prophylaxis is strongly recommended during the radiation phase

Hepatic toxicity including liver failure has been observed in patients enrolled in clinical studies utilizing temozolomide. In addition, liver toxicity may occur several weeks or more after initiation of treatment or after temozolomide discontinuation. For patients with significant liver dysfunction, the risks and benefits of treatment continuation should be carefully considered.

Dose Modifications

Temozolomide During Concomitant Radiation Therapy

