5.7 Primary Endpoints

Phase II Simon Stage 1: No study related undue toxicity or progression in the first stage patients: Toxicity is defined as: progression precluding surgery, unanticipated neurological decompensation, non-completion of neoadjuvant therapy (other than protocol defined dose adjustments or discontinuation), treatment related delay of > 6 weeks to surgery, and/or major unforeseen surgical complication requiring repeat surgical intervention including other than non-life- threatening infection like meningitis/encephalitis or septicemia.

Phase II Stage 2 (Entire Cohort): Progression Free Survival: defined as MRI defined progression (increasing FLAIR, enhancement, diffusion and or perfusion) 3 months after completion of therapy (to allow for excluding pseudo progression) OR clinical progression with new or worsening neurological symptoms related to the tumor (by MRI or clinical correlation with location) and not due to non-tumor or study related symptoms.

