5.9.2 Statistical Power and Sample Size Considerations

In the Simon two-phase design of this study, if:

p_0 = progression rate of Standard of care = 0.5 (null Hypothesis)

p_1 = Progression after study treatment = 0.25

OR

p_0 = non-progression rate of 0.5

p_1 = non-progression rate of 0.75

With a

Prespecified Type I error rate $\alpha \leq 0.05$

Prespecified Power ≥ 0.8

For non-progression being the response:

The null hypothesis that the true response rate $p_0=50\%$ will be tested against a one-sided alternative. In the first stage $n_1=11$ patients will be accrued. If there are $r_1=6$ or fewer patients responding (i.e. don't progress) in these $n_1=11$ patients, the study will be stopped. Otherwise $n-n_1=14$ additional patients will be accrued to a total of $n=25$. The null hypothesis will be rejected if $r_2+1=17$ or more responses (If >17 of 25 patients do not progress in 7 months) are observed in the ($n=25$) patients. This design yields a type I error rate of 0.05 and a power of 80% when the true response rate (non-progression at 7 months) is $>75\%$.

After completion of 25 patients followed at least for 7 months of the last patient treated, Primary and secondary endpoints will be evaluated and reported.

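### Imaging-only progression that cancels resection is a stage 1 failure in section 5.7 but, read literally, is not a primary-endpoint event when it occurs, so the patient can be scored as a 7-month responder

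*Combined protocol and SAP*

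**What the plan says.** Section 5.7 gives two definitions. The stage 1 list begins: "Toxicity is defined as: progression precluding surgery". The definition for the entire cohort has two routes to an event. The imaging route is "MRI defined progression (increasing FLAIR, enhancement, diffusion and or perfusion) 3 months after completion of therapy (to allow for excluding pseudo progression". The clinical route is "OR clinical progression with new or worsening neurological symptoms related to the tumor", and it carries no time restriction. The stage 1 event is not carried into the second definition, and the therapy whose completion starts the 3 months is not named.

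Section 5.9.2 tests the 7-month rate, "For non-progression being the response". The trial stops if 6 or fewer of 11 patients respond and succeeds if 17 or more of 25 do. The start of the 7 months is not stated.

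Sections 5.5.2 and 5.6 schedule an MRI before surgery, so growth at that point would be seen. After that, 5.5.2 sets routine follow-up MRI every two months counted from surgery, and the adjuvant column in 5.6 also starts from surgery. Neither section says when a patient who is never resected is scanned, and no section says how that patient is scored.

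**The concern.** By section 5.5, the experimental element is giving chemoradiation before surgery to patients selected as resectable. Losing the chance of resection because the tumour grew in the meantime is a failure specific to that sequence, and it heads the stage 1 list. If the efficacy count does not register it, the 7-month rate is biased toward the new sequence.

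The Abstract and section 5.1 use the final result to decide whether a randomised phase III trial is warranted. The rule has a fixed cut in 25 patients with no control arm. One misclassified patient can turn 6 of 11 into 7 of 11, or 16 of 25 into 17 of 25.

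Excluding early MRI change because of pseudoprogression is reasonable for a patient who continues as planned. It fits poorly where the change was judged sufficient to abandon the operation.

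**Working it through.** **1. The plan's own figures.** Inputs from 5.9.2: p0 = 0.50, p1 = 0.75, continue if at least 7 of 11 respond, success if at least 17 of 25 respond. With X ~ Bin(11, p) and Y ~ Bin(14, p):

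P(success | p) = Σ (x = 7 to 11) P(X = x) × P(Y ≥ 17 − x)

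At p = 0.50:

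| x | ways, of 2,048 | ways for Y ≥ 17 − x, of 16,384 | product |
|---|---|---|---|
| 7 | 330 | 1,471 | 485,430 |
| 8 | 165 | 3,473 | 573,045 |
| 9 | 55 | 6,476 | 356,180 |
| 10 | 11 | 9,908 | 108,988 |
| 11 | 1 | 12,911 | 12,911 |

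The products sum to 1,536,554. Dividing by 2,048 × 16,384 = 33,554,432 gives 0.0458. At p = 0.75 the same formula gives 0.8005. The stated error rate and power are reproduced. Section 5.9.2 also writes the final cut as more than 17; that version gives 0.020 and 0.701, so 17 or more is used here.

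**2. When the imaging route opens.** Assumption: months run from the start of chemoradiation, because no origin is stated. One month is 365.25/12/7 = 4.348 weeks. Chemoradiation ends at week 6 (30 fractions at five a week) or week 7 (table in 5.6), and surgery falls in weeks 8 to 12. Adjuvant treatment starts 4 to 6 weeks after surgery and runs 6 to 12 cycles of 28 days, with dosing on days 1 to 5 (section 5.5.5).

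- The pre-surgery MRI comes before surgery, so no later than 12/4.348 = 2.76 months.
- Therapy = chemoradiation: 6/4.348 + 3 = 4.38 to 7/4.348 + 3 = 4.61 months.
- Therapy = surgery: 8/4.348 + 3 = 4.84 to 12/4.348 + 3 = 5.76 months.
- Therapy = adjuvant course: shortest (8 + 4 + 5×4 + 5/7)/4.348 + 3 = 10.52 months; longest (12 + 6 + 11×4 + 5/7)/4.348 + 3 = 17.42 months.

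The pre-surgery MRI precedes the opening on all three readings. Time left before month 7 is 7 − 4.38 = 2.62 down to 7 − 5.76 = 1.24 months on the first two readings, and none on the third. A different time origin moves the scan and the opening together, so their order does not change.

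**3. One patient followed through the text.** The pre-surgery MRI shows growth, resection is cancelled, and there are no new tumour-related symptoms.

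- Stage 1 list in 5.7: failure.
- Imaging route: too early. Clinical route: not met.
- Up to month 7: an event is recorded only if symptoms appear, or if a scan happens to be done after the imaging route opens.
- Section 5.9.2: without such a record, the patient is among the "patients responding (i.e. don't progress" group.

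**4. Illustrative size.** Let f be the share of all patients misclassified in this way and still uncounted at month 7. The documents give no value for f. With a true non-progression rate of 0.50, the observed rate is 0.50 + f. The formula in step 1 then gives:

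| f | in 25 patients | observed rate | P(success) | P(stop at stage 1) |
|---|---|---|---|---|
| 0 | 0 | 0.50 | 0.046 | 0.726 |
| 0.02 | 0.5 on average | 0.52 | 0.068 | 0.679 |
| 0.04 | 1 | 0.54 | 0.098 | 0.629 |
| 0.08 | 2 | 0.58 | 0.183 | 0.522 |

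**The case against.** The strongest reply is that the endpoint is binary at 7 months, so a late date does no harm. An event recorded at month 5 rather than month 2.5 still makes the patient a non-responder. On the chemoradiation or surgery reading, growth that was real and never resected might well be recorded in the 1.2 to 2.6 months that remain, by a scan or through symptoms. This stands as a limit: on those readings the effect may be delay rather than loss. It does not close the gap, because routine MRI is counted from surgery and no scan in that interval is assured.

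An analyst might also count the patient as progressed simply because 5.7 calls the event progression. That is a sensible reading, but the cohort definition does not state it.

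Several stronger inferences are tempting, and the documents do not support them:

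- **That all progression before surgery is excluded.** It is not. Symptomatic progression counts at any time, so the gap is confined to imaging-only progression.
- **That the plan directs the wrong score.** It permits that score and gives no instruction for this patient.
- **That protocol treatment must stop and salvage therapy begin.** The clause in 5.5.5, "unless there is evidence of tumor progression or treatment-related toxicity", limits post-operative temozolomide only and is not a rule for an unresected patient.
- **That follow-up is certain to end.** Section 5.4.1 has participation run from "registration to progression, death or 26 months after the enrollment of the last study participant". If the event ends participation as progression, it is hard to call the patient progression-free. If it is not an event, participation need not end. Section 5.4.2 also foresees data from the health record.
- **That failing stage 1 and succeeding in the final count is a contradiction in itself.** The stage 1 list also covers feasibility. A treatment-related delay to surgery of more than 6 weeks fails stage 1 without being progression.
- **That 17% to 24% of patients are affected.** An exponential curve with the 6.9-month standard-of-care median gives 1 − 0.5^(1.84/6.9) = 0.169 and 1 − 0.5^(2.76/6.9) = 0.242 by weeks 8 and 12. That is all progression, not symptom-free growth that cancels surgery.

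**Conclusion.** The point holds for imaging-only progression on the pre-surgery MRI that cancels resection. Section 5.7 treats it as a failure in stage 1 and leaves it outside the cohort definition when it occurs. Whether it is recorded by month 7 depends on an unscheduled scan, on later symptoms, or on an unwritten judgement. On the adjuvant reading of therapy, the imaging route cannot record it by month 7 at all. Any resulting error favours the new sequence.

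The sample-size calculation is correct; the defect lies in how the endpoint is scored. A misclassified share of 2% would already take the false-positive rate to 6.8%, above the prespecified 5%; 4% and 8% give 9.8% and 18.3%. These figures assume a true rate of 50%, the same share in both stages, and that every such patient stays uncounted through month 7. The shares are illustrations, not estimates. The timing assumes a clock that starts with chemoradiation.

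**What to change.** Add one sentence to the entire-cohort definition in 5.7: progression that precludes the planned surgery is a progression event, dated at the MRI or decision that established it, regardless of the 3-month exclusion. Score it the same way in stage 1 and in the 7-month count of 5.9.2.

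Keep the 3-month exclusion for other MRI changes. Define which therapy must be complete and when the 7 months begin, so that MRI events can count before month 7.

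The change affects scoring only and needs no new scan, visit, procedure or patient. Its cost is that an occasional pseudoprogression that led to cancelled surgery will count as a failure, so the observed rate will be slightly less favourable. It also makes an unblinded decision to cancel surgery part of the endpoint, so the imaging basis for each such decision should be recorded.

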5.8 Secondary Endpoints

Overall survival.

5.9 Statistics

The study staff with the assistance of the Biostatistics core, will perform the statistical analysis.

5.9.1 Statistical Analysis Plan

The Simon two-stage design will be used.

The median progression-free survival of these patients with current standard of care therapy is in the range of 6-8 months (6.9 months in the standard of care). With the proposed trial of surgical resection of the tumor after chemotherapy and radiation the median progression free survival is anticipated to be approximately 11-12 months from subset analysis of available literature and based on prior data on other disease sites. In other words, the 7-month local progression rates is anticipated to decrease from 50% to 25%, or progression free survival improve from 50-75% Due to assessment of unanticipated adverse events with this novel sequencing of established treatment, a Simon two-stage phase II study design would be used to proceed with the study treatment after meeting prespecified events in the initial phase, with goal being to determine whether the new treatment paradigm is sufficiently promising to warrant a major controlled clinical evaluation against the standard therapy

5.9.2 Statistical Power and Sample Size Considerations

In the Simon two-phase design of this study, if:

p_0 = progression rate of Standard of care = 0.5 (null Hypothesis)

p_1 = Progression after study treatment = 0.25

OR

p_0 = non-progression rate of 0.5

p_1 = non-progression rate of 0.75

With a

Prespecified Type I error rate $\alpha \leq 0.05$

Prespecified Power ≥ 0.8

For non-progression being the response:

The null hypothesis that the true response rate $p_0=50\%$ will be tested against a one-sided alternative. In the first stage $n_1=11$ patients will be accrued. If there are $r_1=6$ or fewer patients responding (i.e. don't progress) in these $n_1=11$ patients, the study will be stopped. Otherwise $n-n_1=14$ additional patients will be accrued to a total of $n=25$. The null hypothesis will be rejected if $r_2+1=17$ or more responses (If >17 of 25 patients do not progress in 7 months) are observed in the ($n=25$) patients. This design yields a type I error rate of 0.05 and a power of 80% when the true response rate (non-progression at 7 months) is $>75\%$.

After completion of 25 patients followed at least for 7 months of the last patient treated, Primary and secondary endpoints will be evaluated and reported.

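### Section 5.9.2 states the final success rule two ways in one sentence (17 or more, and more than 17, of 25); only 17 or more delivers the stated 80% power, and a count of exactly 17 is left unclassified

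*Combined protocol and SAP*

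**What the plan says.** All the inputs are in section 5.9.2 (Statistical Power and Sample Size Considerations). A response is non-progression, with "p_0 = non-progression rate of 0.5" and "p_1 = non-progression rate of 0.75". The null "will be tested against a one-sided alternative", with prespecified limits of at most 0.05 for type I error and at least 0.8 for power.

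For stage 1: "In the first stage $n_1=11$ patients will be accrued". "If there are $r_1=6$ or fewer patients responding", the study stops; otherwise 14 more patients bring the total to 25.

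The final rule is a single sentence. Its main clause sets the rejection threshold in Simon notation, with r_2+1 equal to 17, and the sentence continues "or more responses (If >17 of 25 patients do not progress in 7 months) are observed". The next sentence gives the operating characteristics: "This design yields a type I error rate of 0.05 and a power of 80% when the true response rate" is above 75%.

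**The concern.** The main clause rejects at 17, 18, and so on up to 25. Read literally, the parenthesis rejects only from 18. The two agree at every count except 17, where one clause declares success and the other does not.

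This threshold decides whether the regimen is judged promising enough for a controlled comparison with standard therapy, the goal given in section 5.9.1. The parenthesis is the only part of the rule expressed in patients and months rather than in design notation. If it were followed, the trial would run at a lower power than the plan states. If the trial ended on exactly 17, the plan's text would not settle the conclusion, and someone would have to choose a reading with the result already known.

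**Working it through.** **Inputs (all from section 5.9.2).** n1 = 11; continue only if 7 or more of 11 respond; 14 further patients, n = 25; p0 = 0.50; p1 = 0.75; final threshold c = 17 (main clause) or c = 18 (parenthesis).

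**Formula.** The exact probability of declaring success at true rate p is

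S(c, p) = sum over x = 7 to 11 of P(X1 = x) × P(X2 ≥ c − x),

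with X1 binomial(11, p) and X2 binomial(14, p). Type I error is S(c, 0.50); power is S(c, 0.75).

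**Power, p = 0.75.**

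| x in stage 1 | P(X1 = x) | P(X2 ≥ 17 − x) | product, c = 17 | P(X2 ≥ 18 − x) | product, c = 18 |
|---|---|---|---|---|---|
| 7 | 0.1721 | 0.7415 | 0.1276 | 0.5213 | 0.0897 |
| 8 | 0.2581 | 0.8883 | 0.2293 | 0.7415 | 0.1914 |
| 9 | 0.2581 | 0.9617 | 0.2482 | 0.8883 | 0.2293 |
| 10 | 0.1549 | 0.9897 | 0.1533 | 0.9617 | 0.1489 |
| 11 | 0.0422 | 0.9978 | 0.0421 | 0.9897 | 0.0418 |
| **Sum** | | | **0.8005** | | **0.7011** |

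**Type I error, p = 0.50.** The same sum gives 0.0458 for c = 17 and 0.0200 for c = 18.

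**The plan's own figures.** With c = 17 the design has type I error 0.0458 and power 0.8005. That reproduces the stated 0.05 (as a rounded or nominal value) and 80%. In a search over two-stage designs with n from 15 to 31 that meet both limits, this one has the smallest expected sample size under p0: 11 + 14 × (1 − 0.7256) = 14.84, where 0.7256 is the probability of stopping after stage 1. It is therefore the Simon optimal design for these rates.

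**The parenthesis.** With c = 18 the power loss is 0.8005 − 0.7011 = 0.0994. Power is 0.777 at a true rate of 0.77 and 0.812 at 0.78, so 80% is reached only at about 0.78.

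**Neighbouring threshold.** With c = 16, type I error is 0.087 and power 0.853. Of 16, 17 and 18, only 17 meets both prespecified limits.

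**Can another assumption rescue more than 17?** No. Ignoring the stage 1 stop gives power 0.727 at c = 18, and relaxing the stage 1 bound to 5 of 11 gives 0.724.

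**How often the conflict would arise.** The probability of passing stage 1 and finishing on exactly 17 is S(17, p) − S(18, p):

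- p = 0.50: 0.0458 − 0.0200 = 0.0258
- p = 0.75: 0.8005 − 0.7011 = 0.0994

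**The case against.** **The intent is recoverable.** This is the strongest reply, and most of it stands. The main clause carries the formal rule, with the r_2+1 notation and an inclusive threshold, and the parenthesis is only a gloss. The stated 80% power follows from 17 and not from 18. That makes the correction safe, but it does not make the text correct: a reader has to know the notation or recompute the design to see which half of the sentence governs.

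**The sign may have lost its underline in PDF conversion.** This is possible but not shown. The inclusive sign survives elsewhere in section 5.9.2, in the prespecified power of at least 0.8. The sponsor can settle it by looking at the source file.

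**Two stronger readings are tempting, and the documents support neither.** A reader might infer that a choice between the thresholds made after the count is known leaves the false-positive rate uncontrolled. It does not: the more lenient reading has type I error 0.0458, so any choice between the two stays at or below that. A reader might also infer that a monitoring committee would apply the parenthesis. Section 6.1 gives the safety board adverse-event data, section 7.3 gives the monitoring committee the review from the feasibility phase to phase II, with a toxicity criterion, and section 5.9 gives the analysis to study staff with the Biostatistics core. No section assigns the final efficacy count to a monitoring body.

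**The Abstract conflicts too.** It gives a different final rule (no more than 9 of 24 progressing in 8 months). That is a separate discrepancy: it does not resolve this one, and aligning the Abstract to section 5.9.2 would leave the contradiction in place.

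**Conclusion.** The point holds as an internal contradiction in the final decision rule. Seventeen or more is the intended threshold. Read literally, the parenthesis describes a different test, with type I error 0.020 and power 0.70, which misses the prespecified power by about 10 points. If the true rate is 75%, there is about a one-in-ten chance that the trial ends on the one count the sentence classifies both ways. The parenthesis errs on the conservative side, so the consequence is lost power and an unclassified result at 17, not an inflated false-positive rate.

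These figures assume 25 evaluable patients, each classified at 7 months, independent outcomes with a common rate, and the 6-of-11 stopping rule applied as written. Because this is the threshold that determines the trial's conclusion, it should be corrected before the final count is known.

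**What to change.** In section 5.9.2, replace the parenthesis with: if 17 or more of 25 patients (8 or fewer failures) are progression-free at 7 months.

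As a minor wording point, state the power condition as a true rate of 75% or more. The 80.05% is obtained at exactly 0.75, the plan's own alternative, not only above it.

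The cost is one line of protocol text, plus the small change to the power sentence. Sample size, stage 1 rule, follow-up and conduct do not change.

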5.4.2 Approximate Duration of Study

We estimate at least 15 patients a year will be enrolled in this study. With further follow-up of at least 26 months from registration to assess the progression free survival, this Phase II study would be completed in 3 years. The end of the study is the last visit of the last subject or end of collection of data from the patient's electronic health record or whichever is last.

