5.6 Study Time and Events Table

Study Procedure	Screening	CRT	Pre-Surgery	Surgery	Adjuvant Treatment for 12 mos. from 4 to 6 weeks after surgery	Follow-up
Study Interval	Day-1 to -21	Weeks 1-7		Weeks 8-12	Every 2 mos. (28 day cycle)	Every 3 mos. after 12 mos. timepoint
Medical history and Examination	X					X
Screening, Labs, pregnancy	X					
Informed consent	X					
Biopsy	X			X		
Temozolomide Dosing ^a	X					X
RT Planning	X					
Radiation Therapy + Temozolomide		X				
Surgery				X		
Adjuvant Temozolomide					X ^e	
MRI	X		X		X	X
Weight	X	X		X	X	X
CBC/d ^b	X	X	X	X	X	X
QOL Questionnaires (MDASI-BT)	X		X		X	X
Concomitant medication Review	X	X			X	X
Adverse events Review ^d	X	X	X	X	X	X

a Temozolomide will continue in the adjuvant setting for a total of 12 weeks

b CBC/d weekly during neoadjuvant CRT +/- 3 days, and pre-surgery

c From the time of informed consent to the end of the study, 26 months.

d. Adjuvant Temozolomide (C1) schedule no later than 4 to 6 weeks from surgery

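### Section 5.9.2 ties overall survival and median PFS to the 7-month cut for the primary test and states no later analysis, although up to 26 months of follow-up is planned

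*Combined protocol and SAP*

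**What the plan says.** Section 5.9.2 closes with the only reporting rule in the plan: "After completion of 25 patients followed at least for 7 months of the last patient treated, Primary and secondary endpoints will be evaluated" and reported. The sentence covers primary and secondary endpoints together. Section 5.8 lists one secondary endpoint, "Overall survival".

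Section 5.4.1 expects that "the median overall survival is in the order of 14-18 months". It defines participation as running from "registration to progression, death or 26 months after the enrollment of the last study participant". Section 5.4.2 speaks of completing the study "With further follow-up of at least 26 months from registration to assess the progression free survival", and a footnote to the table in section 5.6 reads "From the time of informed consent to the end of the study, 26 months".

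Section 5.1 makes a significant median PFS the basis for a phase III trial, and section 4.3 (Aim 2) asks for PFS and for the effect of local control on OS. Section 5.9.1 anticipates a median PFS of about 11-12 months. The documents give no second data cut, minimum number of deaths or analysis method for OS.

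**The concern.** The 7-month trigger comes from the primary endpoint, non-progression at 7 months in 25 patients. By then every patient has passed the landmark, so the binary test is complete. A median is different: its precision depends on how much of the survival curve has been observed. For the last patient, 7 months is 39-50% of one expected OS median (7/18 to 7/14).

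Followed as written, the rule allows the trial's only OS result, and the only estimate of median PFS, to be reported when the point estimate usually exists but its upper confidence limit usually does not. The additional follow-up that would supply the limit is planned, but no analysis is tied to it. Because the time is a minimum and not a date, the cut could also be chosen after survival data have been seen.

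**Working it through.** **The plan's own figure.** Section 5.9.2 uses n1 = 11 (continue if more than 6 do not progress), n = 25, reject at 17 or more, p0 = 0.50, p1 = 0.75. The rejection probability is the sum over x = 7 to 11 of P(X1 = x) × P(X2 ≥ 17 − x), with X1 ~ Bin(11, p) and X2 ~ Bin(14, p). This gives alpha = 0.0458 and power = 0.8005, which agrees with the stated 0.05 and 80%. OS does not enter this calculation.

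**Inputs for OS.**
- 25 patients (5.9.2) at 15 a year (5.4.2): 25/15 × 12 = 20 months of accrual.
- Median OS m = 14 to 18 months (5.4.1).
- Cut c = 7 or 26 months after the last enrollment.
- My assumptions: exponential survival, steady entry, no loss to follow-up, vital status known after progression.

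**Expected deaths.** With uniform entry over A = 20 months, the share dead is 1 − [m/(A ln 2)] × [2^(−c/m) − 2^(−(c+A)/m)].
- c = 7, m = 14: 1 − 1.010 × (0.707 − 0.263) = 0.551, or 13.8 of 25.
- c = 7, m = 18: 1 − 1.298 × (0.764 − 0.354) = 0.467, or 11.7 of 25.
- c = 26, m = 14: 1 − 1.010 × (0.276 − 0.103) = 0.825, or 20.6 of 25.
- c = 26, m = 18: 1 − 1.298 × (0.367 − 0.170) = 0.744, or 18.6 of 25.

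With entry at fixed 0.8-month intervals (0 to 19.2 months), follow-up at the early cut is 7 to 26 months, mean 16.6. Expected deaths are then 13.6, 12.4 and 11.5 for m = 14, 16 and 18, and 20.5, 19.5 and 18.5 at the later cut.

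**Precision of the median.** Kaplan-Meier curves with log-log 95% limits, 4,000 simulated trials per setting:

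| Cut after last enrollment | Median reached | Upper 95% limit estimable |
|---|---|---|
| 7 months, m = 14 to 18 | about 92% to 75% | 28-38% (m = 14) to 10-17% (m = 18) |
| 26 months, m = 14 to 18 | over 99% | 97-98% (m = 14) to 82-84% (m = 18) |

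The ranges within cells reflect differences between runs in entry pattern and in how the limit is computed.

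For PFS with an 11.5-month median, the upper limit is estimable in 51-57% of trials at 7 months and in about 100% at 26 months.

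**Sensitivity of the 7-month figures.**
- Accrual of 10 months (the 3 years in 5.4.2 less 26 months): 9.2-11.1 deaths, median reached in 35-61%, upper limit in 3-8%.
- Accrual paused 7 months for the stage 1 decision: mean follow-up 19.3 months, median reached in 91-98%, upper limit in 59%, 44% and 31% for m = 14, 16 and 18.
- The 7 months counted from about 3 months after enrollment (a 10-month cut): 53-61% dead instead of 47-55%.

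**Does the planned follow-up supply the later deaths?** Two points limit it.
- Section 5.4.1 ends participation at progression. With an exponential median PFS of 11-12 months, the share past progression at 26 months is 1 − 2^(−26/12) = 78% to 1 − 2^(−26/11) = 81%.
- The 26 months is defined in more than one way. If it means 26 months per patient and not 26 months after the last enrollment, expected deaths are 25 × (1 − 2^(−26/m)) = 18.1 (m = 14) to 15.8 (m = 18), so the gain is smaller.

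**The case against.** The best defence is that 5.9.2 sets a floor. Reporting at 26 months would satisfy both 5.9.2 and 5.4.2. A reader might infer that the two sections contradict each other on analysis time. The documents do not support that: 5.4.2 gives a length of follow-up, linked to PFS, and no analysis date. What stands is narrower: the earliest permitted time is too early for OS, and nothing commits the trial to a later one.

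A reader might also infer that the phase III decision would rest on immature OS. It would not. The Abstract and section 5.1 base that decision on progression, and OS appears there only as a phase III endpoint. In this trial OS is untested.

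Nor can it be said that OS is not estimable at 7 months. Staggered entry means about half the patients will have died, and the median is reached in most simulated trials. If accrual pauses between stages, the upper limit is also available more often (31-59%). With 25 patients the interval stays wide at any cut.

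Finally, a later cut is not free. Most patients would have left the study at progression by then, and no section commits to survival follow-up afterwards. This objection stands in full and has to be part of the fix.

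**Conclusion.** The point holds as a recommended clarification and does not touch the validity of the primary test. At the minimum time in 5.9.2, about 11-14 of 25 deaths are expected. The OS median usually has a point estimate but an upper 95% limit in only about 10-38% of trials. At 26 months after the last enrollment, 18-21 deaths are expected and the limit is available in about 82-98%.

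These figures assume exponential survival with the plan's 14-18 month median, 15 patients a year without a pause, no loss to follow-up, and vital status known after progression. Faster accrual makes the early cut worse and a between-stage pause makes it better. In both cases the later cut gives more deaths and a more usable interval. Median PFS, which section 5.1 names as the basis for phase III, gains in the same way.

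**What to change.** Split the last sentence of 5.9.2:

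1. The 7-month primary endpoint is tested when the 25th patient has 7 months of follow-up.
2. The final OS and median PFS analyses are done at 26 months after the last enrollment. Any OS result given earlier is labelled interim.

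In 5.4.1, state that vital status is collected after progression up to the OS cut, for example from the electronic health record that 5.4.2 already names as a data source. Give the 26 months one definition across 5.4.1, 5.4.2 and the footnote in 5.6. Correct the 3-year duration too, since 20 months of accrual plus 26 months is 46 months.

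Cost: protocol wording and a small amount of vital-status collection. The go/no-go result is not delayed. The final OS report comes about 19 months after it (26 − 7).
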